9.2	Abbreviations.....	14
10	REFERENCES	15

STATEMENT OF COMPLIANCE

The trial will be conducted in accordance with International Conference on Harmonisation Good Clinical Practice (ICH GCP) and applicable United States (US) Code of Federal Regulations (CFR). The Principal Investigator will assure that no deviation from, or changes to, the protocol will take place without prior documented approval from the Institutional Review Board (IRB), except where necessary to eliminate an immediate hazard(s) to the trial subjects. All personnel involved in the conduct of this study have completed Human Subjects Protection and ICH GCP Training.

The protocol, informed consent form(s), recruitment materials, and all subject materials will be submitted to the local Institutional Review Board (IRB) for review and approval. Approval of both the protocol and the consent form must be obtained before any subject is enrolled. Any amendment to the protocol will require review and approval by the IRB before the changes are implemented to the study. All changes to the consent form will be IRB approved; a determination will be made regarding whether a new consent needs to be obtained from subjects who provided consent, using a previously approved consent form.

1 PROTOCOL SUMMARY

1.1 SYNOPSIS

Title:	Spectacle lenses in concussed kids
Study Description:	Many kids who have sustained a concussion still experience symptoms months after the event. This study will examine if certain types of lenses in glasses will help alleviate those symptoms.
Objectives:	Compare symptoms of concussed kids after wearing different types of glasses, one of which is a control.
Endpoints:	3 month follow up phone call
Study Population:	9-17 year olds who have sustained a concussion and are symptomatic
Phase:	3
Description of Study Intervention:	Different types of glasses lenses that are already commercially available and are used routinely in concussion patient.
Study Duration:	2-3 years, largely dependent on ability to recruit subjects
Subject Duration:	3 months

1.2 SCHEDULE OF ACTIVITIES (SOA)

1. Participants are recruited through routine eye exams at concussion clinic
2. If a patient is eligible for study, an investigator will reach out to the patient at that time to present patient with the opportunity to enroll in the study. The patient has 1 week from that date to decide.
3. Once consents are signed and subject is officially enrolled, they will be randomized into 1 of 3 possible lens options.
4. Investigators will then order the lenses from the supplier to then be fit in patient's glasses
5. Dispense of glasses to participant (timing will vary due to dependence on supplier). Repeat concussion survey at dispense.

6. Masked in-person exam 4-6 weeks from dispense of glasses
 - a. Standard binocular vision assessment for primary and secondary measurements
7. Last assessment: 3 month phone call after dispense of glasses for last concussion survey

2 INTRODUCTION

2.1 STUDY RATIONALE

The main goal for this study is to determine the effectiveness of anti-fatigue (low additional prescription at near) in treating post-concussion patients for their visual symptoms. The main outcome measurement will be the convergence insufficiency symptom survey (CISS) pre-intervention and post-intervention of the anti-fatigue lenses. This will be compared to the CISS results of single vision glasses (rule out placebo effects)

Other secondary outcome measurement will be objective measurements of vergence ranges and accommodation magnitude and flexibility, reduction of symptoms with single vision glasses alone for low refractive error individuals and the effects of anti-reflective coating.

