4 STUDY POPULATION

4.1 INCLUSION CRITERIA

- 9-17 years of age
- Sustained a concussion ≥ 6 weeks ≤ 16 weeks from date of ophthalmic exam
 - Criteria for concussion: clinically diagnosed by physician
- Best corrected visual acuity: 20/30 in both eyes at near; 20/25 in each eye at distance
- Minimum Stereopsis: 500" global
- CISS score ≥ 16
- Refractive error at least $\pm 0.50D$ sphere or cylinder
- Ability to clear ≥ 0.50 cycles per minute in monocular accommodative flipper of and binocular accommodative flipper

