5.1.2 DOSING AND ADMINISTRATION

Dosing is the same throughout treatment arms. Participants are expected to wear the glasses regardless of treatment arm every day. This would be self-administrated.

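### The symptom reduction listed as a secondary outcome for single vision glasses has no comparator in the described design, so a fall within that arm cannot be credited to the lenses

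*Protocol*

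**What the plan says.** Section 2.1 (Study Rationale) makes the CISS before and after anti-fatigue lenses the main outcome and sets it against single vision: "This will be compared to the CISS results of single vision glasses (rule out placebo effects"). The next paragraph lists, as a secondary outcome, "reduction of symptoms with single vision glasses alone for low refractive error individuals". No comparator is attached to it.

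The rest of the document describes these arms and measurements:

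- Section 1.1: "Compare symptoms of concussed kids after wearing different types of glasses, one of which is a control". The control is thus a pair of glasses.
- Section 1.2: after consent, "they will be randomized into 1 of 3 possible lens options".
- Section 5.1.2: "Participants are expected to wear the glasses regardless of treatment arm every day".
- Section 4.1: entry requires "CISS score ≥ 16", with the concussion 6 to 16 weeks before the eye exam and a refractive error of at least ±0.50 D. Low refractive error is not defined.
- Section 1.2: "Repeat concussion survey at dispense"; then an in-person masked exam at 4 to 6 weeks; then "Last assessment: 3 month phone call after dispense of glasses for last concussion survey".

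Section 8.1 makes the CISS score the efficacy endpoint and leaves the secondary endpoints to be determined. Section 8.3.3 does the same for their analysis. No section says whether the exam score or the dispense score is the baseline.

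**The concern.** A reduction of symptoms with one kind of glasses alone reads as a response to those glasses. To estimate such a response, the trial would need children who did not get them, followed over the same time. The described randomised contrasts are all between lens types, so they show how lenses differ from each other and not what single vision glasses do in themselves.

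Three other causes push the score down in this arm. Children are admitted because they score high on the outcome scale, which brings regression to the mean. They are followed for 3 months after dispense while they may still be recovering. And the arm is there because a placebo response is expected in it.

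An analyst can choose any test for this outcome later, but no choice of test supplies the missing group. If the fall were read as benefit, it would feed the advice to doctors and families on prioritising treatment that section 2.3.2 promises.

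**Working it through.** The plan has no figure of its own to reproduce: section 8.2 bases the sample size on funding and gives no effect, SD, alpha or power. What follows shows orders of magnitude under assumptions.

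**1. Is there a contrast?** Sections 1.1, 1.2 and 5.1.2 together give three lens options, a control that is one of them, and daily wear in all. No untreated or delayed-glasses group is described. The outcome in section 2.1 is thus, as far as the document goes, a change within one arm.

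**2. Regression to the mean from the entry cut.** From the protocol: threshold 16. Assumed: CISS normal in the screened population with mean μ = 20 to 30, SD 10, test-retest correlation ρ = 0.7 to 0.9. With a = (15.5 − μ)/SD, treating scores as whole points,

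expected fall = (1 − ρ) × SD × φ(a)/(1 − Φ(a)).

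- μ = 20: a = −0.45; φ/(1 − Φ) = 0.3605/0.6736 = 0.535. Fall = 0.3 × 10 × 0.535 = 1.61 (ρ = 0.7) or 0.1 × 10 × 0.535 = 0.54 (ρ = 0.9).
- μ = 30: a = −1.45; 0.1394/0.9265 = 0.150. Fall = 0.45 or 0.15.

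Selection alone thus gives about 0.2 to 1.6 points. With a wider grid (mean 16 to 28, SD 8 to 12, ρ 0.6 to 0.9, cut at 16) the range is 0.1 to 3.8 points.

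**3. How often would a paired test find a fall with zero lens effect?** From the protocol: 90 participants (section 3.2) and three arms, so 90/3 = 30 per arm if allocation is equal, which is not stated. Assumed: 15 children in a low refractive error subgroup; a total non-lens fall D of 2, 4 or 6 points; SD of change 8 or 10; two-sided 5% one-sample t-test. The noncentrality is (D/SD) × √n, and the critical values are 2.045 (29 df) and 2.145 (14 df). For example, D = 4, SD 10, n = 30 gives 0.4 × 5.477 = 2.19 and a rejection rate of 56%.

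| Non-lens fall | n = 30, SD 8 | n = 30, SD 10 | n = 15, SD 8 | n = 15, SD 10 |
|---|---|---|---|---|
| 2 points | 26% | 19% | 15% | 11% |
| 4 points | 75% | 56% | 44% | 30% |
| 6 points | 98% | 89% | 77% | 58% |

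The nominal rate is 5%. All cells exceed it, but the spread is wide and is driven by D, for which the protocol gives no value.

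**4. What does the dispense survey change?** It is not used for selection. If its correlation with the exam score is about the same as that of the later score, the expected fall due to selection has already happened by dispense and drops out of the dispense-to-follow-up change. If correlation decays with time, a small part remains. Recovery and placebo response after dispense are untouched.

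**The case against.** The strongest reply is that section 2.1 offers a clause in a rationale, not an analysis. It prescribes no test and makes no causal statement, and the secondary endpoints and their analysis are still open. This stands in part. A reader might infer that the trial will very likely report that plain glasses reduce symptoms. The document does not support that: it is an inference from wording, and the rates above hang on assumed CISS parameters. At a 2-point fall they are only 19 to 26% (n = 30) or 11 to 15% (n = 15). What does not stand is that a later analysis plan could settle the matter, since no described arm supplies the contrast.

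The clause goes on to the effects of anti-reflective coating, so single vision alone might mean single vision without coating, as one side of a randomised comparison. The arms are not defined well enough to exclude this. But such a contrast would estimate the coating effect, and still not the effect of single vision glasses.

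Nor is it a contradiction to describe change in a control arm; that is routine. The difficulty is only in attributing it.

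Two further readings are tempting. One is that the final phone call adds a change of survey mode to the within-arm change. The document does not state how the survey is given at the exam or at dispense, and an in-person exam for primary and secondary measurements falls at 4 to 6 weeks, so this is not established. The other is that the exam-to-dispense change could serve as a no-lens reference. It cannot: that interval carries the regression to the mean, its length depends on the supplier, and nothing bars children from wearing glasses they already own.

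Finally, section 2.2 gives no recovery rate for the 6 to 16 week window. Its 73% still symptomatic is at 4 weeks, before entry opens, and it speaks of slow resolution. So recovery after entry is plausible, and its size is unknown.

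**Conclusion.** The point holds as a limit on what can be concluded from one secondary outcome. As described, the design has no randomised contrast that isolates single vision glasses, and at least three non-lens causes could readily lower the CISS in that arm. The bias cannot be sized from the protocol. The illustrative rejection rates of 19 to 98% at n = 30 and 11 to 77% at n = 15 assume a 2 to 6 point non-lens fall, SD of change 8 to 10, equal allocation, and a subgroup of 15. The absence of a group without glasses is read from the lens-option wording, because the three arms are not fully specified. The randomised comparison of anti-fatigue with single vision lenses is not affected: these non-lens causes are expected to act alike in both arms.

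**What to change.** In section 2.1, reword the outcome along these lines: *change in CISS from dispense in low refractive error participants in the single vision arm, described without attribution to the lenses*. Keep the low refractive error restriction, and say what low means.

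Name the survey already scheduled at dispense as the baseline for this change, in place of the eligibility score, and state that it is the CISS (section 1.2 says only concussion survey). This removes most of the regression to the mean, but not recovery or placebo response, so the change stays descriptive.

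Reserve statements of effect for randomised contrasts between lens types. Do not present the exam-to-dispense change as a no-lens control.

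The cost is a few lines of text, with no new visit, arm or participant. The price is a weaker claim for single vision glasses, which the described design could not have supported.

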2.2 BACKGROUND

The CDC estimated that over half of the traumatic brain injury (TBI) emergency room visits were for patients 14 years and younger in 2010¹. The actual incidence may be even higher due to unreported TBIs. Mild TBIs or concussions are the most common form of TBIs. There has been a recent increase in interest to understanding the effects of concussions on young patients. Children who sustain concussions tend to have worse and prolonged symptoms compared to adults². These chronic symptoms commonly affect their cognitive ability, and mental and physical health.

A number of studies have set out to determine the associated symptoms and the prevalence and duration of those symptoms. One study measured 73% of 247 concussed children 5-18 years old were still symptomatic 4 weeks post-concussion and 61% reported a decline in grades³. Many studies⁴⁻⁵ agree that one of most common symptoms is visual complaints such as blurred vision and light sensitivity. There have been many studies documenting reduced accommodation and convergence in post-concussion patients⁵⁻⁶. Gallaway⁵ measured 47% and 42% of concussion patients had convergence insufficiency and accommodative insufficiency, respectively. The slow resolution of these visual disorders may lead to disruptions in learning, many children requiring a median of 12 days before returning to part time school³.

Now that there is more knowledge of the repercussions from concussion, it is imperative that we continue to learn how to effectively treat and manage these disorders since the number of concussions is predicted to increase over the years. As of now, there is no standard of care or published effective treatment for binocular and accommodative issues for patients after a concussion. More standardized and objective concussion assessment and post-concussion treatment are needed in research.

2.3 RISK/BENEFIT ASSESSMENT

2.3.1 KNOWN POTENTIAL RISKS

None. This study minimizes risk to the participant by using non-invasive procedures already being done as part of standard clinical eye care practice. Visual acuity, stereoacuity, ocular alignment, and other visual efficiency testing are done as part of standard practice. Unmasked investigators will be available to address these risks, allowing discontinuation of study treatment to pursue other interventions if needed. It is the investigator's opinion that the protocol's level of risk falls under DHHS46.404, which is research not involving greater than minimal risk. Although no adverse events are anticipated as a result of this treatment, all adverse events will be reported.

2.3.2 KNOWN POTENTIAL BENEFITS

It is possible that some of the patients might find resolution of symptoms depending on the treatment arm. The results of this research may change or help guide the treatment of concussion patients by providing evidence-based treatment results. Given the extensive costs related to concussion management and the cost of progressive addition lenses compared to typical glasses prescribed for children, this prospective project will help doctors and families make decisions on prioritizing treatment options following concussion.

3 STUDY DESIGN

3.1 OVERALL DESIGN

This is a multi-site clinical trial (Identifier: NCT03123822) including Boston Children's Hospital, Salus University Pennsylvania College of Optometry, [name] private practice, Akron Children's Hospital, and the University of Alabama at Birmingham (coordinating site). All sites have identical study designs: a prospective randomized group comparison observational study with a masked examiner to treatment arm.

3.2 END OF STUDY DEFINITION

A participant is considered to have completed the study if he or she has completed all phases of the study including the last visit or the last scheduled procedure shown in the Schedule of Activities (SoA), Section 1.3.

The study is considered finished when the study has enrolled 90 participants total or if enrollment is too difficult or with too many adverse effects, then study may be terminated at the discretion of the principal investigator.

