7.2.4 TIME PERIOD AND FREQUENCY FOR EVENT ASSESSMENT AND FOLLOW-UP

The occurrence of an adverse event (AE) or serious adverse event (SAE) may come to the attention of study personnel during study visits and interviews of a study subject presenting for medical care, or upon review by a study monitor.

All AEs including local and systemic reactions not meeting the criteria for SAEs will be captured on the appropriate case report form (CRF). Information to be collected includes event description, time of onset, clinician's assessment of severity, relationship to study product (assessed only by those with the training and authority to make a diagnosis), and time of resolution/stabilization of the event. All AEs occurring while on study must be documented appropriately regardless of relationship. All AEs will be followed to adequate resolution.

Any medical condition that is present at the time that the subject is screened will be considered as baseline and not reported as an AE. However, if the study subject's condition deteriorates at any time during the study, it will be recorded as an AE.

Changes in the severity of an AE will be documented to allow an assessment of the duration of the event at each level of severity to be performed. AEs characterized as intermittent require documentation of onset and duration of each episode.

The Study Coordinator will record all reportable events with start dates occurring any time after informed consent is obtained until 7 (for non-serious AEs) or 30 days (for SAEs) after the last day of study participation. At each study visit, the Study Coordinator will inquire about the occurrence of AE/SAEs since the last visit. Events will be followed for outcome information until resolution or stabilization.

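### Section 3.2 confuses close of enrolment with end of study: the study is called finished at the 90th enrolment, when that child has no glasses and is at least 3 months from the last survey

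*Protocol*

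**What the plan says.** Protocol section 3.2 (End of Study Definition) contains two definitions.

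- For a participant: "A participant is considered to have completed the study if he or she has completed all phases of the study", which the section takes to include the last visit or last procedure in the schedule.
- For the study: "The study is considered finished when the study has enrolled 90 participants total". The same sentence goes on to allow early termination by the principal investigator.

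Section 1.2 (Schedule of Activities) fixes where enrolment falls in the sequence: "Once consents are signed and subject is officially enrolled, they will be randomized into 1 of 3 possible lens options". After that come lens ordering and dispense, whose timing is left to the supplier. Then follow "Masked in-person exam 4-6 weeks from dispense of glasses" and "Last assessment: 3 month phone call after dispense of glasses for last concussion survey".

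The synopsis (1.1) gives the endpoint as "3 month follow up phone call", the study duration as 2-3 years and the subject duration as 3 months. Section 7.2.4 records adverse events for 7 days (non-serious) or 30 days (serious) "after the last day of study participation".

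No other section ends the study at the last participant's last assessment. Sections 6.1 and 9.1.2 deal only with early termination or suspension.

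**The concern.** The study-level rule uses an enrolment target as the end of the study. On the day the 90th child enrols, that child is not yet randomised and has no glasses. Other recently enrolled children are still short of their exam, their call or both. Those children can meet the participant-level definition only after the study is, by its own definition, over.

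If a site or data manager applied the sentence literally, the most recent enrollees would lack the assessment that the synopsis names as the endpoint, and fewer than 90 children would be evaluable at 3 months. Section 9.1.5.2 also counts the minimum 3-year record retention from the completion of the study, so that clock could start before the last children's data exist. The wording deserves care because section 3.1 lists five sites and section 5.3 has a new resident run the study each year.

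**Working it through.** **Plan's own figure.** The 90 cannot be reproduced: section 8.2 attributes the sample size to funding and gives no statistical inputs. The check does not depend on how 90 was reached.

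**Order of events (no assumption needed).** Consent signed and enrolled, then randomised, lenses ordered, glasses dispensed, exam at dispense + 4-6 weeks, call at dispense + 3 months. The time from enrolment to the call is therefore supply lag + 3 months, which is never less than 3 months. Consent time does not enter, because section 1.2 item 3 puts signed consent before enrolment.

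**Inputs for the count**
- N = 90 (section 3.2).
- Duration D = 24 to 36 months (section 1.1).
- Follow-up F = 3 months to the call, or 4-6 weeks to the exam (section 1.2).
- Supply lag L: not given. Assumed range 0 to 6 weeks; 6 / 4.345 = 1.38 months.
- Accrual: assumed uniform.

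**Formulas.** With w = L + F, the number of children who have not reached the assessment at the 90th enrolment is:
- Reading A (D ends at the 90th enrolment): 90 × w / D.
- Reading B (D also contains the last child's follow-up, so accrual is shorter): 90 × w / (D − w).

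**Children without the 3-month call**

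| Lag | D (months) | Reading A | Reading B |
|---|---|---|---|
| 0 | 36 | 90 × 3/36 = 7.5 (8.3%) | 90 × 3/33 = 8.2 (9.1%) |
| 0 | 24 | 90 × 3/24 = 11.25 (12.5%) | 90 × 3/21 = 12.9 (14.3%) |
| 6 weeks | 36 | 90 × 4.38/36 = 11.0 (12.2%) | 90 × 4.38/31.62 = 12.5 (13.9%) |
| 6 weeks | 24 | 90 × 4.38/24 = 16.4 (18.3%) | 90 × 4.38/19.62 = 20.1 (22.3%) |

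**Children without the 4-6 week exam.** The same formulas give about 2.3 to 5.5 with no lag and 5.8 to 11.7 with a 6-week lag. Some children who lack the call would therefore already have had the exam.

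**Effect of the correction on the end date.** The last child's call falls 3.0 to 4.4 months after the 90th enrolment for a lag of 0-6 weeks. Adding the 30-day serious-event window (about 1 month) gives roughly 4.0 to 5.4 months.

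**The case against.** The best reply is that nothing in the protocol makes follow-up depend on the study still being open. Section 1.2 schedules dispense, exam and call for each enrolled child. The first sentence of 3.2 defines completion by the last procedure, section 6.3 requires active efforts to regain contact, and section 7.2.4 follows adverse events to resolution. Read together, 90 is an enrolment target carelessly phrased. This stands as to consequence: a reader might infer that the protocol plans to abandon the last children, and the documents do not support that. It does not repair the sentence, which sits under a heading that says it defines the end of the study and which no other section corrects.

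Three further inferences should be resisted.

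- *That the trial would lose its only endpoint.* The synopsis lists the 3-month call, but section 8.1 names the CISS (convergence insufficiency symptom survey) score without a time point. Section 1.2 item 6a places primary and secondary measurements at the 4-6 week exam.
- *That losses would fall more heavily on certain lens types or sites.* The protocol says dispense timing depends on the supplier; it does not say that timing differs by lens or site.
- *That the adverse-event windows are voided.* They run from each participant's own last day, so they are not cancelled by a study-level label, although they do extend past the stated end.

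**Conclusion.** Section 3.2 is wrong as written: it states the close of enrolment as the end of the study and does not fit the participant-completion definition beside it. That follows from the protocol's own schedule.

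The loss is conditional on literal application. What is then certain is that at least the last-enrolled child lacks the exam and the 3-month call. The wider counts rest on uniform accrual, on how the 2-3 year duration is read and on a supply lag that the documents do not give. They run from about 7.5-11 of 90 (8-13%) with no lag and accrual filling the stated duration, to about 20 of 90 (22%) with an assumed 6-week lag and follow-up contained within 24 months.

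**What to change.** Replace the study-level sentence in section 3.2 with:

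> Enrolment closes when 90 participants have been enrolled. The study is finished when the last enrolled participant has completed, or can no longer complete (withdrawn or lost to follow-up), the 3-month survey and the adverse-event reporting period of 7.2.4.

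Keep the early-termination clause as a separate sentence. Two small points in the same amendment: section 3.2 cites the schedule as Section 1.3, but it is headed 1.2; and because section 6.2 allows replacement of randomised children who never receive glasses, say whether the 90 counts them.

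Cost: a short protocol amendment with ethics-board approval, and no new procedures or participants. The formal study end moves by at least 3 months plus supply time and the adverse-event reporting window after the last enrolment, and the record-retention period starts correspondingly later.
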